Patients with unresectable or metastatic cutaneus melanoma with measurable disease, whose disease has progressed following at least 1 line of standard of care immunotherapy including an anti-PD-1/ anti-PD-L1 antibody.

Inclusion criteria

Patients who meet all of the following criteria will be eligible to participate in the study:

- 1. Must provide written informed consent for the study;
- 2. Must be able to comply with the Protocol as judged by the Investigator;
- 3. Are ≥18 years of age on day of signing informed consent;
- 4. Have histologically confirmed Stage 3 (unresectable) or Stage 4 (metastatic) CM, as per the American Joint Committee on Cancer staging system, eighth edition;
- 5. Have documented radiological progression on prior systemic therapy;
- 6. Have previously received anti-PD-1/L1 as monotherapy or in combination. A maximum of 2 prior lines of systemic therapy is allowed for BRAF wild-type disease and a maximum of 3 prior lines of systemic therapy is allowed for BRAFV600 positive disease;
 - Note: Adjuvant treatment is considered as a line of therapy only if patient experienced relapse/progression on therapy or within 6 months from adjuvant therapy completion;
- 7. Have measurable disease based on Response Evaluation Criteria in Solid Tumors (RECIST) version 1.1 (hereinafter, RECIST);
- 8. Have a performance status of 0 or 1 on the Eastern Cooperative Oncology Group (ECOG) Performance Status;
- 9. Have adequate organ functions as defined in Table TS4:

Table TS4. Adequate Organ Function Laboratory Values

System	Laboratory Value
Hematological	
ANC	≥1500/µL
Platelets	≥100,000/µL
Hemoglobin	≥9 g/dL or ≥4.96 mmol/L
Renal	
Measured or calculated[1] CrCl (GFR can also be used in place of CrCl)	≥30 mL/min
Hepatic	
Serum total bilirubin OR direct bilirubin	≤1.5 × ULN OR ≤1.5 × ULN for patients with total bilirubin levels >1.5 × ULN; direct bilirubin ≤1.5 × ULN for patients with Gilbert's syndrome
AST (SGOT) or ALT (SGPT)	\leq 2.5 × ULN OR \leq 5 × ULN for patients with liver metastases
Albumin	>2.5 g/dL

Table TS4. Adequate Organ Function Laboratory Values (Continued)

- 1. CrCl should be calculated per Cockcroft-Gault equation.
- ALT = alanine aminotransferase; ANC = absolute neutrophil count; AST = aspartate aminotransferase; CrCl = creatinine clearance; GFR = glomerular filtration rate; SGOT = serum glutamic oxalacetic transaminase; SGPT = serum glutamic pyruvic transaminase; ULN = upper limit of normal.

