4.1 Inclusion Criteria

Patients who meet all of the following criteria will be eligible to participate in the study:

- 1. Must provide written informed consent for the study;
- 2. Must be able to comply with the Protocol as judged by the Investigator;
- 3. Are \geq 18 years of age on day of signing informed consent;
- 4. Have histologically confirmed Stage 3 (unresectable) or Stage 4 (metastatic) CM, as per the American Joint Committee on Cancer staging system, eighth edition;
- 5. Have documented radiological progression on prior systemic therapy;
- 6. Have previously received anti-PD-1/L1 as monotherapy or in combination. A maximum of 2 prior lines of systemic therapy is allowed for BRAF wild-type disease and a maximum of 3 prior lines of systemic therapy is allowed for BRAFV600 positive disease;

Note: Adjuvant treatment is considered as a line of therapy only if patient experienced relapse/progression on therapy or within 6 months from adjuvant therapy completion;

- 7. Have measurable disease based on RECIST;
- 8. Have a performance status of 0 or 1 on the ECOG Performance Status;
- 9. Have adequate organ functions as defined in Table 9:

Table 9. Adequate Organ Function Laboratory Values

System	Laboratory Value
Hematological	
ANC	≥1500/μL
Platelets	≥100,000/μL
Hemoglobin	≥9 g/dL or ≥4.96 mmol/L
Renal	
Measured or calculated ¹ CrCl (GFR can also	
be used in place of CrCl)	≥30 mL/min
Hepatic	
	\leq 1.5 × ULN OR \leq 1.5 × ULN for patients with total bilirubin
	levels >1.5 × ULN; direct bilirubin \leq 1.5 × ULN for patients with
Serum total bilirubin OR direct bilirubin	Gilbert's syndrome
AST (SGOT) or ALT (SGPT)	$\leq 2.5 \times \text{ULN } \underline{\text{OR}} \leq 5 \times \text{ULN for patients with liver metastases}$
Albumin	>2.5 g/dL

^{1.} CrCl should be calculated per Cockcroft-Gault equation.

ALT = alanine aminotransferase; ANC = absolute neutrophil count; AST = aspartate aminotransferase; CrCl = creatinine clearance; GFR = glomerular filtration rate; SGOT = serum glutamic oxalacetic transaminase; SGPT = serum glutamic pyruvic transaminase; ULN = upper limit of normal.

- 10. Female patients of childbearing potential must have a negative serum pregnancy test at the Screening Visit and a negative (urine or serum) pregnancy test within 72 hours prior to study Day 1. If the urine test is positive or cannot be confirmed as negative, a serum pregnancy test will be required and must be negative for the patient to be eligible;

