Transient elevation of hepatic transaminases are observed with ANV419 and are considered to occur in the context of IL-2 mediated AEs. The transient elevations are usually asymptomatic, mild or moderate in severity, typically not associated with increased total bilirubin and alkaline phosphatase, resolve spontaneously without treatment, and are predominantly occurring in the first two cycles. For AST and/or ALT elevations beyond cycle 2, and for AST/ALT elevations in the

context of total bilirubin increase, follow the adverse event management guidance for hepatitis (Table 15).

Table 14: Management guidelines for AST and/or ALT elevations with early onset related to ANV419

	Recommended management	Dose modification
AST or ALT > 3 but ≤ 5 × ULN	 LFT monitoring: Repeat lab every 3 days If no improvement within 7 days, initiate treatment with steroids Consider imaging for obstruction Exclude non-inflammatory etiologies 	Withhold ANV419 until ≤ Grade 1 or baseline; continue at same dose
AST or ALT > 5 × but ≤ 8 × ULN	 LFT monitoring: Repeat lab every 3 days If no improvement within 7 days, initiate treatment with steroids Consider adding non-corticosteroid immunotherapy 	Withhold ANV419 until ≤ Grade 1 or baseline; continue at same dose
AST or ALT > 8 × ULN	 LFT monitoring: Repeat lab every 1-2 days If no improvement within 7 days, initiate treatment with steroids Consider adding non-corticosteroid immunotherapy Consult gastroenterologist 	Consider permanent discontinuation of ANV419

Hepatitis

Table 15: Management guidelines for hepatitis related to ANV419

(adapted from the ASCO management guidelines for Immune-Related Adverse Events; J Clin Oncol2021:36 4073-4126).

CTCAE v5.0	Recommended management	Dose modification
Grade 1	• Close monitoring (1-2 ×	Continue ANV419 at same dose
Asymptomatic (AST or	weekly)	
ALT > ULN to $3.0 \times$	• Exclude alternate etiologies	
ULN and/or total	(e.g., viral hepatitis, alcohol	
bilirubin > ULN to 1.5 ×	hepatitis)	
ULN	1 /	

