Grade 2 Asymptomatic (AST or ALT > 3.0 to ≤ 5.0 × ULN and/or total bilirubin > 1.5 to ≤ 3.0 × ULN) Grade 3 AST or ALT 5.0-20.0 × ULN and/or total bilirubin 3-10 × ULN, OR symptomatic liver dysfunction; fibrosis by biopsy; compensated cirrhosis; and reactivation of chronic hepatitis	 Stop unnecessary medication and any potential hepatotoxic drugs Consider administration of steroids if no improvement in 3-5 days Increase monitoring frequency to every 3 days Consider adding mycophenolate mofetil if no improvement after 3 days Consider hepatology consult for Grade 2 and above Start steroids 1-2 mg/kg methylprednisolone or equivalents Consider liver biopsy Monitor labs daily 	Withhold ANV419 until ≤ Grade 1; continue at same dose Permanently discontinue ANV419
Grade 4 AST or ALT > 20.0 × ULN and/or total bilirubin > 10 × ULN OR decompensated liver function	Consider adding methylprednisolone 2 mg/kg/d equivalents	Permanently discontinue ANV419

Note: Combination of AEs suggestive of drug induced liver injury (DILI), with hepatocellular injury (AST or ALT $> 3.0 \times ULN$) accompanied by evidence of impaired hepatic function (total bilirubin elevation $> 2 \times ULN$), in the absence of evidence of initial biliary obstruction (i.e., significant elevation of ALP) or some other explanation of the injury (e.g., viral hepatitis, alcohol hepatitis), see FDA guidance, should lead to permanent discontinuation from treatment.

Other adverse events

For other adverse events deemed as clinically significant and for which no specific guidelines are provided, the following dose modifications should be followed (Table 16).

Table 16: Management guidelines for "other" ANV419 related adverse events

CTCAE v5.0	Dose modification
Grade 1	Continue at the same dose of ANV419
Grade 2	If tolerable: Continue at the same dose of ANV419;
	If intolerable: withhold ANV419 until \leq Grade 1 or baseline;
	reinstate ANV419 at the same dose
Grade 3	Withhold ANV419 until ≤ Grade 1 or baseline;
	1 st occurrence: reinstate ANV419 at the same dose
	2 nd occurrence or if not manageable: permanently discontinue if
	3rd occurrence: permanently discontinue ANV419
Grade 4	Permanently discontinue ANV419

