All other irAEs	Persistent Grade 2	Withhold. Upon	Withhold. Upon resolution to	Based on severity of AE, administer	Ensure adequate evaluation to

Anaveon AG Clinical Study Protocol ANV419-101

		resolution to ≤Grade 1, may resume study treatment.	≤Grade 1, may resume study treatment.	corticosteroids.	confirm etiology or exclude other causes.
	Grade 3	Withhold or discontinue based on the event. ⁰	Withhold or discontinue based on the event. ⁰		
	Recurrent Grade 3 or Grade 4	Permanently discontinue.	Permanently discontinue.		

Table 18. Dose Modification for ANV419 in Combination With Pembrolizumab (Continued)

Note: Non-irAEs will be managed as appropriate, following clinical practice recommendations.

AST/ALT = >3 to $5 \times \text{ULN}$ if baseline is normal; >3 to $5 \times \text{baseline}$, if baseline is abnormal; bilirubin: >1.5 to $3 \times \text{ULN}$ if baseline is normal; >1.5 to $3 \times \text{baseline}$ if baseline is abnormal.

AST/ALT: >5 to $20 \times$ ULN if baseline is normal; >5 to $20 \times$ baseline, if baseline is abnormal; bilirubin: >3 to $10 \times$ ULN if baseline is normal; >3 to $10 \times$ baseline if baseline is abnormal.

AST/ALT: $>20 \times$ ULN if baseline is normal; $>20 \times$ baseline, if baseline is abnormal; bilirubin: $>10 \times$ ULN if baseline is normal; $>10 \times$ baseline if baseline is abnormal.

The decision to withhold or permanently discontinue pembrolizumab is at the discretion of the Investigator or treating physician. If control is achieved or resolution to \leq Grade 2, pembrolizumab may be resumed.

Events that require discontinuation include, but are not limited to, encephalitis and other clinically important irAEs (eg, vasculitis and sclerosing cholangitis).

AE = adverse event; ALT = alanine aminotransferase; AST = aspartate aminotransferase; DRESS = drug reaction with eosinophilia and systemic symptoms; GI = gastrointestinal; irAE = immune-related adverse event; IV = intravenous(ly); NCI CTCAE = National Cancer Institute Common Terminology Criteria for Adverse Events; SJS = Stevens-Johnson syndrome; T1DM = type 1 diabetes mellitus; TEN = toxic epidermal necrolysis; ULN = upper limit of normal.

Source: Keytruda®. Package Insert. Merck Sharp & Dohme Corp; 2014

Table 19. Dose Modification for ANV419 in Combination With Ipilimumab

	C 1			C 4: 4 :1	
	Grade			Corticosteroid	
	(NCI CTCAE	Action with	Action with	and/or Other	Monitoring and
irAEs	Version 5.0)	ANV419	Ipilimumab	Therapies	Follow-Up

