Pneumonitis	Grade 2 Recurrent Grade 2, Grade 3 or 4	Withhold. Upon resolution to ≤Grade 1, may resume study treatment. Withhold study treatment. Upon resolution to ≤Grade 1, may resume study treatment 1 dose level lower.	Withhold. Upon resolution to ≤Grade 1, may resume study treatment. Permanently discontinue.	Administer corticosteroids (initial dose of 1 to 2 mg/kg prednisone or equivalent) followed by taper. Add prophylactic antibiotics for opportunistic infections.	Monitor participants for continuing signs and symptoms of pneumonitis. Evaluate participants with radiographic imaging.

Table 19. Dose Modification for ANV419 in Combination With Ipilimumab (Continued)

Table 19. Dose	Modification 10	or AN V 419 in	Combination V	Vith Ipilimumab	(Continuea)
irAEs Diarrhea/colitis	Grade (NCI CTCAE Version 5.0) Grade 2 Recurrent Grade 3 or Grade 4	Action with ANV419 Withhold. Upon resolution to ≤Grade 1, may resume study treatment.	Action with Ipilimumab Withhold. Upon resolution to ≤Grade 1, may resume study treatment.	Corticosteroid and/or Other Therapies Administer corticosteroids (initial dose of 1 to 2 mg/kg prednisone or equivalent) followed by taper.	Monitoring and Follow-Up Monitor participants for continuing signs and symptoms of enterocolitis (ie, diarrhea, abdominal pain, blood or mucus in stool with or without fever) and of bowel perforation (ie, peritoneal signs and ileus). Participants with ≥Grade 2 diarrhea suspected colitis should consider GI consultation and performing endoscopy to rule out colitis. Participants with diarrhea/colitis should be advised to drink liberal quantities of clear fluids. If sufficient oral fluid intake is not feasible, fluid and electrolytes should be substituted via IV infusion.
AST or ALT elevation or increased bilirubin	AST/ALT >3 to 5 × ULN or total bilirubin is more than 1.5 × and up to 3 × ULN AST/ALT >5 × ULN or total bilirubin is more than 3 × ULN	Withhold. Upon resolution to ≤Grade 1, may resume study treatment. Permanently discontinue.	Withhold. Upon resolution to ≤Grade 1, may resume study treatment. Permanently discontinue.	Administer corticosteroids (initial dose of 0.5 to 1 mg/kg prednisone or equivalent) followed by taper. Administer corticosteroids (initial dose of 1 to 2 mg/kg prednisone or equivalent) followed by taper.	Monitor with liver function tests (consider weekly or more frequently until liver enzyme value returned to baseline or is stable).

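### The liver-test dose rules use different reference values and resume conditions for patients whom the entry criteria admit with abnormal AST/ALT

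*Protocol*

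**What the plan says.** **Entry.** Table 9 in Protocol Section 4.1 caps AST/ALT at 2.5 × ULN, relaxed to "5 × ULN for patients with liver metastases"; the synopsis has the same limit in Table TS4. It applies to every arm.

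**Monotherapy (Section 5.4.5.1).** Table 14 covers early AST/ALT rises in Cycles 1 and 2. The text before it sends other cases to Table 15: "For AST and/or ALT elevations beyond cycle 2, and for AST/ALT elevations in the" context of a bilirubin increase. Table 15 is headed CTCAE v5.0 and sets its bands by ULN alone: "Grade 2 Asymptomatic (AST or ALT > 3.0 to ≤ 5.0 × ULN and/or total bilirubin > 1.5 to ≤ 3.0 × ULN", then "Grade 3 AST or ALT 5.0-20.0 × ULN and/or total bilirubin 3-10 × ULN". The actions for those two rows, in order, are "Withhold ANV419 until ≤ Grade 1; continue at same dose Permanently discontinue ANV419". For its two lower bands Table 14 accepts either Grade 1 or baseline before dosing resumes. Table 16, for other events, accepts the same. Table 15 does not mention baseline.

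**Combination arms (Section 5.4.5.4).** Table 18 (Arm B) is also headed CTCAE version 5.0: Grade 2 means withhold, Grade 3 or 4 means permanently discontinue. Its footnotes use ULN when baseline is normal and multiples of baseline when it is not; the Grade 3 footnote includes "baseline, if baseline is abnormal; bilirubin: >3 to". Table 19 (Arm C) uses ULN only, with permanent discontinuation at "AST/ALT >5 × ULN or total bilirubin is more than 3 × ULN". Both tables have a column for the action on ANV419.

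**Which rule applies.** Section 5.4.5.4 says both drugs are held according to Tables 18 and 19 for the events listed there, whatever the attribution. It then refers events clearly attributable to ANV419 to Section 5.4.5, which contains Tables 14 and 15. Its general text lets an immune-related event resolve to baseline or to Grade 1 or lower, and makes a hold of more than 42 days permanent.

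**SAP 3.8.2** grades abnormal laboratory results by NCI-CTCAE version 5 and tabulates shifts from baseline to worst grade. It names no reference for an abnormal baseline.

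**The concern.** The entry rule deliberately admits patients whose transaminases are already raised. For them the choice between ULN and baseline as reference decides whether a given rise has no consequence, interrupts dosing or ends treatment. Two tables with the same grading label make that choice differently, and the text does not settle which applies in Arm B.

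The resume condition raises a second problem, and it lies in the part of the trial that was run. A patient who starts above 3 × ULN can recover fully to the entry value and still fail a condition that asks for Grade 1 or lower. A hold that cannot end becomes permanent: after more than 42 days in the combination arms, and after a maximum delay (blacked out in the public copy) in monotherapy.

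At stake are consistent handling of patients with abnormal entry values, the interpretation of discontinuations for liver tests, and the laboratory grades reported under SAP 3.8.2.

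**Working it through.** The plan gives no figure to reproduce. The check runs one AST or ALT value, in multiples of ULN, through each table as written.

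**Inputs.** Entry limit 5 × ULN with liver metastases, 2.5 × ULN without (Table 9). Tables 15 and 19: withhold above 3 and up to 5 × ULN, permanently discontinue above 5 × ULN. Table 18 with abnormal baseline b: Grade 2 (withhold) above 3 × b, Grade 3 (permanently discontinue) above 5 × b. Table 14: withhold above 3 and up to 8 × ULN, consider permanent discontinuation above 8 × ULN.

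**Thresholds (× ULN).**

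| Baseline b | Tables 15 and 19: permanent stop above | Table 18: withhold above 3 × b | Table 18: permanent stop above 5 × b |
|---|---|---|---|
| 1 (normal) | 5 | 3 | 5 |
| 2 | 5 | 6 | 10 |
| 2.5 | 5 | 7.5 | 12.5 |
| 3 | 5 | 9 | 15 |
| 4 | 5 | 12 | 20 |
| 5 | 5 | 15 | 25 |

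With a normal baseline the three tables agree. With an abnormal one they separate. Tables 15 and 19 stop treatment permanently while Table 18 read alone lists no action for values above 5 × ULN and up to 3 × b. That window exists once 3 × b exceeds 5, so b above 5/3 = 1.67 × ULN. It can therefore also arise without liver metastases, since 1.67 is below the 2.5 × ULN limit.

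**Example 1: reference value.** Baseline 4 × ULN, drug-related rise to 6 × ULN after Cycle 2; 6/4 = 1.5 × baseline.
- Table 15: Grade 3, permanently discontinue.
- Table 19: above 5 × ULN, permanently discontinue.
- Table 18: 1.5 is below 3, and Grade 2 starts above 3 × 4 = 12 × ULN.
- Table 14, had the rise come in Cycles 1 or 2 without a bilirubin increase: withhold.

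The permanent-stop thresholds are 5 and 5 × 4 = 20 × ULN, a factor of 4; at b = 5 the factor is 25/5 = 5.

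**Example 2: resume condition, Part 1.** Baseline 4 × ULN, related rise to 4.8 × ULN, return to 4 × ULN.
- In Cycles 1 or 2 without a bilirubin increase, Table 14 withholds and the return to baseline meets its resume condition.
- After Cycle 2, Table 15 Grade 2 withholds and asks for Grade 1 or lower, which it defines as up to 3 × ULN. The value 4 does not meet it.

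This gap needs a baseline above 3 × ULN and a peak no higher than 5 × ULN, because a higher peak falls in the permanent-stop row.

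**Arm C.** Table 19 asks for Grade 1 or lower. The general text of Section 5.4.5.4 also accepts baseline. For the patient in Example 2 the two passages give different answers.

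**The case against.** Several stronger readings are tempting, and the documents do not support them.

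- *Patients are stopped for values at their entry level.* Table 15 concerns hepatitis related to ANV419, and Section 7.1 does not count a condition present at Screening as an adverse event unless it changes. A stable 4 × ULN triggers nothing, so both examples use a related rise.
- *Arm B would take no action at 6 × ULN.* That follows only from Table 18 read alone. If the event is clearly due to ANV419, Section 5.4.5.4 points to Section 5.4.5 and so to Table 15. Section 4.4 also allows stopping for a severe laboratory abnormality and requires it under Hy's law. What stands is that the governing rule is unclear.
- *Nobody in Arm C could resume at baseline.* The general text of Section 5.4.5.4 allows it. The defect is the disagreement with Table 19.
- *Comparison between arms was damaged.* Parts 2 and 3 never opened (SAP Sections 1 and 5), Arms A1 and A2 share the same tables, and SAP 3.1.4 plans no formal testing.

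Three further defences carry weight. Section 5.4.5.1 describes its guidance as not rigid and subordinate to clinical judgement. It says transaminase rises occur mainly in the first two cycles, where Table 14 governs unless bilirubin also rises. And the tables cite different sources: Table 15 an oncology society guideline, Tables 18 and 19 the partner drugs' package inserts. A difference between arms may therefore be intended. But Tables 18 and 19 also set the action for ANV419, and nothing in the protocol says a difference is meant. None of these defences explains why Table 15 omits the return-to-baseline option that Tables 14 and 16 give in the same section.

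**Conclusion.** The point holds as an inconsistency in wording with practical consequences for a limited group. Tables 15 and 18 carry the same grading label but grade an abnormal baseline differently. At a baseline of 4 × ULN their permanent-stop thresholds are 5 and 20 × ULN, and the table that governs in Arm B is not settled. In Part 1, a patient with baseline above 3 × ULN and a related rise within the Table 15 Grade 2 band cannot meet its resume condition by returning to baseline, although Table 14 would accept that.

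The conclusion assumes that the tables are applied as written, that the rise is judged drug-related and, for Table 15, that it occurs after Cycle 2 or with a bilirubin increase. The documents do not say how many patients enter with abnormal transaminases, so no frequency can be given. The conflict involving Arms B and C remained on paper; the Table 14/15 mismatch and the silence of SAP 3.8.2 concern the part that ran. Which reference or resume rule is clinically right is not judged here.

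**What to change.** Reconcile Table 9, Tables 14 to 16, Table 18 with its footnotes, Table 19 and the attribution and resumption text of Section 5.4.5.4. Three things should be stated without contradiction: the reference value for patients with abnormal baseline liver tests, the condition for resuming, and the table that governs in the combination arms when an event is attributed to ANV419. If a difference between arms is intended, say so. The sponsor's medical team decides the rule.

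In SAP 3.8.2, add a sentence naming the grading reference used when baseline is abnormal. If the database is already locked, the clinical study report can carry it, as SAP Section 1 provides for later deviations.

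The cost is wording. No extra tests are needed: AST and ALT are in the safety chemistry panel, the safety laboratory is scheduled at Screening, and SAP 3.1.2 already defines baseline. Because the trial stopped after Part 1, the combination-arm changes matter only if those parts or their tables are used again.

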5.4.5.2 Management of adverse immune-related adverse events in monotherapy arms

Investigators should monitor patients for potential irAEs. Once an AE is detected, it should be followed until resolution. An irAE can occur shortly after the first dose of ANV419 or several months after the last dose. For clinical management of irAEs, Investigators should follow the consensus guidelines provided by National Comprehensive Cancer Network[®], ³⁴ American Society of Clinical Oncology[®], ³⁵ and European Society for Medical Oncology^{36,37}.

